7.3.4.1 Adverse Events

AEs will be coded by system organ class and preferred term using the *Medical Dictionary for Regulatory Activities* (MedDRA), Version 21.0 or newer.

An AE will be considered a treatment-emergent adverse event (TEAE) if the AE began or worsened (increased in severity or became serious) on or after the first dose of OL IP.

The number and percentage of patients reporting TEAEs during the OL treatment period will be tabulated by system organ class and preferred term, by system organ class, preferred term, and severity, and by system organ class, preferred term, and relationship to IP.

The number and percentage of patients reporting TEAEs during the DB treatment will be tabulated for each treatment group by system organ class and preferred term, by system organ class, preferred term, and severity, and by system organ class, preferred term, and relationship to IP.

The number and percentage of patients reporting TEAEs during the SFU period will be tabulated by system organ class, preferred term, and DB treatment group for the DB safety population and by system organ class and preferred term for the OL safety follow-up population.

For the OL period, DB period, or SFU period, if more than 1 AE was coded to the same preferred term for the same patient, the patient will be counted only once for that preferred term using the most severe and most related occurrence for the summarization by severity and by relationship to IP.

The total number and percentage of TEAEs during the DB treatment period will also be summarized by severity and relationship to IP for each treatment group.

The number and percentage of patients with common ($\geq 2\%$ of patients in any treatment group) TEAEs during the DB treatment period will be summarized by preferred term and treatment group.

An AE that occurs more than 30 days after the last dose of DB IP will not be summarized.

An SAE that occurred between the date of the first dose of IP and 30 days after the date of the last dose of IP, inclusive, will be considered an on-therapy SAE. The number and percentage of patients who had on-therapy SAEs during the OL treatment period and the OL SFU period will be summarized by preferred term. The number and percentage of patients who had on-therapy SAEs during the DB treatment period and the DB SFU period will be summarized by preferred term and DB treatment group.

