6.7 DOUBLE-BLIND INTENT-TO-TREAT POPULATION

The DB ITT population will consist of all patients who took at least 1 dose of DB IP and had at least 1 post-randomization assessment of the PANSS or CGI-S scores during the DBTP of the study.

Patients will be included in the randomized treatment group for the DB ITT population.

7.0**STUDY PATIENTS****7.1****PATIENT DISPOSITION**

The OLTP starts with the first dose of OLTP and ends with one of the following: the last scheduled assessment at the Visit 13/end of OLTP (Week 18) or early termination (ET) before Visit 13 (Week 18) for patients who do not enter the DBTP; or 1 day before the first dose of DBTP (or the date of the first dose of the DB IP if the last scheduled assessment date in the OLTP is on the date of the first dose of the DBTP) for patients who enter the DBTP.

The DBTP starts with the first day of randomization and ends with the last scheduled assessment at Visit 26 (Week 44) or ET.

The SFU period starts one day after the end of the previous period and ends with the last available assessment. For patients without Visit 27 (Week 46) or Visit 28 (Week 48) assessment, the SFU period would not be derived.

Screen-failure patients (ie, patients screened but not included in the OL Safety Population) and the associated reasons for failure will be tabulated overall for the Screened Population.

The number and percentage of patients in the Screened, OL Safety and OL ITT Populations will be summarized overall and by study center. The number and percentage of patients in the Randomized, DB Safety, and DB ITT Populations will be summarized overall by treatment group and by treatment group and study center.

The number and percentage of patients in the OL Safety Population, who prematurely discontinued from the OLTP, who completed the OLTP, who entered the DBTP, and who entered the SFU period will be summarized overall and by reasons for premature discontinuation as recorded on the respective disposition pages of the electronic case report form (eCRF).

Similarly, the number and percentage of patients in the DB Safety Population who completed the DBTP, who prematurely discontinued from the DBTP, and who entered the SFU period will be summarized overall, by DB treatment group and by reasons for premature discontinuation as recorded on the respective disposition pages of the eCRF. Patients who relapse during the DBTP will also be summarized as completing the study.

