11.0 SAFETY ANALYSES

The safety analyses will be performed for the OL safety, OL SFU and DB safety populations. The summarization will be overall for the OLTP in the OL safety population and OL SFU period in the OL SFU population, and by treatment group for the DB period and the DB SFU period in the DB safety population. The summarization for the OLTP will use the OL safety population as the denominator. The summarization for the DBTP will use the DB safety population as the denominator. The summarization for the OL SFU period or DB SFU period will use the OL SFU population or the DB safety population as the denominator respectively.

Safety parameters will include adverse events (AEs), clinical laboratory parameters, vital signs, Electrocardiographic (ECG) parameters, ophthalmological parameters, Columbia–Suicide Severity Rating Scale (C-SSRS), and EPS scales, including Abnormal Involuntary Movement Scale (AIMS), Barnes Akathisia Rating Scale (BARS), and Simpson-Angus Scale (SAS).

For each safety parameter, the last assessment made before the first dose of OL IP will be used as the baseline for all analyses of that safety parameter, unless stated otherwise. Continuous variables will be summarized by number of patients and mean, SD, median, minimum, and maximum values. Categorical variables will be summarized by number and percentage of patients.

The derived visits in the DBTP will use the same strategy as described in Section 10.0. The detailed week mapping windows is provided in Section 16.1.

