11.1 ADVERSE EVENTS

AEs will be coded by system organ class and preferred term using the *Medical Dictionary for Regulatory Activities* (MedDRA), Version 21.1 or newer.

An AE will be considered a treatment-emergent adverse event (TEAE) if the AE began or worsened (increased in severity or became serious) on or after the date of the first dose of OL IP. Per eCRF instructions, a new AE record will be created with a new AE onset date for any AE that worsens. Therefore, TEAEs can simply be identified as those AEs with recorded onset date (and time, if known) on or after the date of the first dose of IP.

The number and percentage of patients reporting TEAEs during the OLTP will be tabulated by system organ class and preferred term; by system organ class, preferred term, and severity; and by system organ class, preferred term, and relationship to IP.

The number and percentage of patients reporting TEAEs during the DBTP will be tabulated for each treatment group by system organ class and preferred term; by system organ class, preferred term, and severity; and by system organ class, preferred term, and relationship to IP. The total number and percentage of TEAEs during the DBTP will also be summarized by severity and relationship to IP for each treatment group.

The number and percentage of patients reporting TEAEs during the OL SFU period will be tabulated by system organ class and preferred term for the OL Safety Population. The number and percentage of patients reporting TEAEs during the DB SFU period will be tabulated by system organ class, preferred term, and DB treatment group for the DB Safety Population.

For OLTP, DBTP, or SFU period, if more than 1 AE was coded to the same preferred term for the same patient, the patient will be counted only once for that preferred term using the most severe and most related occurrence for the summarization by severity and by relationship to IP.

An AE that occurs more than 30 days after the date of the last dose of DB IP or occurs after the last SFU visit (whichever comes last) will not be summarized except for AEs related to reported pregnancies. AEs associated with pregnancies reported in the protocol-required timeframe up to approximately 12 weeks following the last dose of DB IP will be summarized.

The number and percentage of patients with common ($\geq 2\%$ of patients in any treatment group) TEAEs will be summarized by preferred term for OLTP and be summarized by preferred term and treatment group for DBTP.

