
The number and percentage of TEAEs leading to premature discontinuation of IP during the OLTP will be summarized by preferred term. The incidence of AEs leading to premature discontinuation of IP during the DBTP will be summarized by preferred term and treatment group.

An AE will be considered a TESAE if it is a TEAE that additionally meets any SAE criterion.

Summary tables will be provided for patients with TESAEs if these occurred in 5 or more patients. The number and percentage of patients with TESAEs will be summarized for OLTP, DBTP, and SFU period.

For the Screened Population, listings will be presented for patients with SAEs, patients with AEs leading to premature discontinuation, and patients who die (if any). All patients with SAEs, including SAEs reported during the screening period and the SFU period, and patients discontinuing because of AEs occurring before the start of OLTP will be included in these listings.

The number and percentage of patients with any EPS TEAEs, EPS SAEs, and EPS AEs leading to premature discontinuation of IP will be summarized overall for the OLTP in the OL safety population and by treatment for the DBTP in the DB safety population separately.

The number and percentage of patients reporting TEAEs of ocular events of special interest will be summarized overall for the OLTP in the OL safety population and OL SFU period in the OL SFU population, by treatment for the DBTP and DB SFU in the DB safety population. A listing of all reported ocular events of special interest will be provided.

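### SAP 7.1 derives no follow-up period for patients with neither Visit 27 nor Visit 28, so recorded events inside the SAP 11.1 cut-off can have no table cell; separately, one SAP 11.1 sentence names the wrong population for open-label follow-up TEAEs

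*SAP*

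**What the plan says.** **Periods.** SAP 7.1 (Patient Disposition) closes the open-label period of a patient who is not randomised, and the double-blind (DB) period, at the last scheduled or early termination (ET) visit. On follow-up it says "The SFU period starts one day after the end of the previous period and ends with the last available assessment", and then "For patients without Visit 27 (Week 46) or Visit 28 (Week 48) assessment, the SFU period would not be derived". The second sentence is read here as meaning neither visit, because SAP 6.4 asks for at least one follow-up visit. Reading it as missing either visit would widen the gap described below.

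**Cut-off.** SAP 11.1 leaves out of the summaries any event that falls "more than 30 days after the date of the last dose of DB IP or occurs after the last SFU visit (whichever comes last"). Pregnancy-related AEs are exempt and are kept to about 12 weeks after the last DB dose. The protocol's own rule in 7.3.4.1 is also tied to the DB dose: "An AE that occurs more than 30 days after the last dose of DB IP will not be summarized".

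**Tables.** SAP 11.1 and Appendix IV tabulate TEAEs, TESAEs and ocular events by open-label, DB and follow-up period. Neither describes a table over all periods.

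**Population for open-label (OL) follow-up.** One SAP 11.1 sentence reads "TEAEs during the OL SFU period will be tabulated by system organ class and preferred term for the OL Safety Population". SAP 11.0 says that summaries for the "OL SFU period or DB SFU period will use the OL SFU population or the DB safety population as the denominator". The ocular paragraph of SAP 11.1 summarises "overall for the OLTP in the OL safety population and OL SFU period in the OL SFU population". Protocol 7.3.4.1 tabulates follow-up TEAEs "by system organ class and preferred term for the OL safety follow-up population", and protocol 7.3.4 agrees.

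**The concern.** The SAP has two rules for events after treatment. The 11.1 cut-off runs by date and needs no visit. The 7.1 period needs a visit and stops at the last assessment. The tables need a period, so an event that the cut-off means to keep can have nowhere to go.

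This matters mainly for SAEs and ocular AESIs, because those are recorded whether or not the patient returns. Protocol 9.3 requires SAE reporting for at least 30 days after the last dose, and protocol 6.5.2 requires ocular AESIs to be reported within 24 hours of the site learning of them. Other AEs are mainly elicited at visits (protocol 9.1.1). Whether a reported event after drug withdrawal enters an incidence table would then depend on the patient attending follow-up.

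The population sentence is a separate matter. The OL Safety Population includes randomised patients, who cannot have an OL follow-up event, so using it would dilute every OL follow-up TEAE percentage.

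**Working it through.** **1. Follow one event.** Take a DB patient whose last dose is on the day of the ET visit, with no follow-up visit and an SAE 20 days later.
- SAP 7.1: the DB period ended at ET and no SFU period is derived.
- SAP 11.1 cut-off: 20 is less than 30, so the event is not excluded.
- SAP 11.1 tables: by period only, so there is no cell for it.
- SAP 11.0: the patient still counts in the DB safety denominator.

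SAP 17.0 says the TESAE timeframe is aligned with the date-based cut-off. The 7.1 periods do not deliver that.

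**2. Length of the gap for a DB patient.** Let k be the days from last dose to the ET or final visit, and v the days from that visit to the last SFU visit (0 if none). SFU visits are due 2 and 4 weeks after that visit (protocol 8.8), within 3 days either way (protocol Table 2).

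Uncovered days = max(0, 30 − k − v)

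| Follow-up attended | v (window) | k = 0 | k = 4 (assumed) |
|---|---|---|---|
| Neither visit | 0 | 30 | 26 |
| Visit 27 only | 14 (11 to 17) | 16 (19 to 13) | 12 |
| Both visits | 28 (25 to 31) | 2 (5 to 0) | 0 |

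The second and third rows arise because 7.1 ends the period at the last available assessment, taken here as the last SFU visit.

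**3. OL-only patients.** The 11.1 cut-off refers to the last DB dose or the last SFU visit. An OL-only patient with no SFU visit has neither date. SAP 6.4 also leaves this patient out of the OL SFU population; protocol 7.1.4 does not.

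**4. Denominator for OL follow-up TEAEs.** Inputs from SAP 14.0: 345 randomised, 33.3% of OL patients randomised, 34% screening failure, 1035 OL patients and 1569 screened.
- Plan's figures: 345 / 0.333 = 1036, or 345 × 3 = 1035, against 1035 stated; 1035 / (1 − 0.34) = 1568, against 1569 stated. Both reproduce to rounding.
- Largest possible OL SFU population, assuming all 1035 are dosed: 1035 − 345 = 690.
- Ratio: 1035 / 690 = 1.50.
- Example: 10 patients with an event give 10 / 690 = 1.45% or 10 / 1035 = 0.97%.
- In general the minimum understatement is 1 / (1 − s), where s is the randomised share. The study ended early, so s may differ. Over an assumed range: 1.11 at 10%, 1.25 at 20%, 1.50 at the planned 33.3%.

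**5. Weight of one event.** One unassigned patient in a planned DB arm of 115 is 1 / 115 = 0.87%, about 0.9 percentage points.

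**The case against.** The strongest reply is that the loss is inferred. SAP 7.1 concerns disposition, SAP 11.1 never cites it and carries its own date rule, and the SAP places table specifications in a separate document. A programmer who followed the cut-off alone would keep the day-20 SAE. This stands in part: the defect is a conflict between two rules, and the unseen specifications may resolve it. But 7.1 is the only period definition in the SAP, and the SFU windows in Table 16-1 are noted as being for vital signs. Nothing in the SAP says in which table that SAE belongs.

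Other limits stand:
- TESAE summary tables are produced only if events occur in 5 or more patients, so there may be no such table either way.
- The only scheduled eye examination in follow-up is at Visit 28, for patients with a post-baseline cataract finding. Ocular events in non-attenders would have to come from spontaneous reports.
- The last available assessment could be an unscheduled visit, which would shorten the gap.
- For OL-only patients without a visit, SAP 6.4 and 7.1 at least drop numerator and denominator together.
- The DB potential Hy's Law summary already runs by date to 30 days after the last DB dose and is unaffected.

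Three stronger readings are tempting but unsupported. A reader might infer that post-withdrawal events vanish from the report; the SAP keeps listings of SAEs, deaths, AEs leading to discontinuation, ocular events and all AEs. A reader might infer that OL follow-up percentages will be wrong; that follows only if the 11.1 sentence is applied over the explicit denominator rule in 11.0. A reader might infer that the narrower OL SFU population was undisclosed; Appendix V item 4 records it, although Section 17.0 does not.

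**Conclusion.** Both points hold on the text and should be fixed. Applying SAP 7.1 and 11.1 together leaves recorded events inside the cut-off with no table cell, over up to 30 days for a DB patient with no SFU visit. This rests on reading the 7.1 sentence as neither visit and on the table specifications not supplying another rule. Follow-up attendance and event counts after ET are not in the documents, so no share of lost events can be stated; the uncovered days are not an estimate of bias.

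The population sentence contradicts SAP 11.0, the 11.1 ocular paragraph and protocol 7.3.4 and 7.3.4.1. If followed, it understates OL follow-up TEAE percentages by a factor of at least 1 / (1 − s), which is 1.5 on planned numbers.

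Appendix IV retains the OL and DB follow-up summaries of TEAEs, TESAEs and ocular events, so both points carry into the abbreviated report. Safety is descriptive and efficacy is unaffected.

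**What to change.** - For AE tables, define the SFU period by date for every treated patient who does not continue to the next treatment period: from the day after the last treatment period to the later of 30 days after the last dose of IP (OL or DB) or the last SFU visit, whether or not Visit 27 or 28 took place.
- Write the SAP 11.1 cut-off with the same reference to the last dose of IP (OL or DB).
- Assign to that SFU period the pregnancy-related AEs that 11.1 already keeps to about 12 weeks; otherwise they would still lack a period.
- In the 11.1 sentence on OL follow-up TEAEs, replace the OL Safety Population with the OL SFU population. For AE tables, define that population as in protocol 7.1.4 (all non-randomised OL safety patients), so that inclusion never depends on having an event.
- If the SAP 6.4 visit condition is kept for visit-based summaries such as vital signs, record the departure from the protocol in Section 17.0.

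The cost is SAP wording and minor reprogramming. SAEs and ocular AESIs are reportable regardless of attendance, so no new data are needed for them. Non-serious events that were never collected cannot be recovered this way.

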7.2 PROTOCOL DEVIATIONS

The number and percentage of patients with important protocol deviations will be summarized overall for the OLTP, and by treatment group for the DBTP. Supportive listings will also be provided. At a minimum, deviations related to the following categories will be included:

- Inclusion or exclusion criteria
- Withdrawal criteria
- Treatment or dose
- Concomitant medications

These and any additional important protocol deviations will be reviewed and documented before database lock and unblinding of treatment codes.

8.0**DEMOGRAPHICS AND OTHER BASELINE CHARACTERISTICS**

Demographic parameters (age; age group; region; race; ethnicity; sex; weight; height; and body mass index [BMI], calculated as weight [kg]/(height [m])²) and other baseline characteristics (medical and surgical history, psychiatric disorders, , and nondrug psychiatric treatment) will be summarized descriptively overall for the OL Safety and OL ITT Populations and by treatment group for the DB Safety and DB ITT Populations.

The baseline efficacy variables for OL TP, which is defined as the last available assessment at or prior to the first dose of OL IP, will be summarized descriptively overall for the OL ITT Population. The baseline efficacy variables for DBTP, which is defined at the last available assessment at or prior to the first dose of DB IP, will be summarized by treatment for the DB ITT Population.

Continuous variables will be summarized by number of patients and mean, standard deviation (SD), median, Q1, Q3, minimum, and maximum values. Categorical variables will be summarized by number and percentage of patients.

Prior medication is defined as any medication started before the date of the first dose of OL IP. *Concomitant medication* during the OLTP is defined as any medication taken on or after the date of the first dose of OL IP during the OLTP. *Concomitant medication* during the DBTP is defined as any medication taken on or after the date of the first dose of DB IP during the DBTP.

The use of prior and concomitant medications during the OLTP will be summarized by the number and percentage of patients receiving each medication within each therapeutic class for the OL Safety Population. The use of concomitant medications during the DBTP and SFU period will be summarized by treatment group by the number and percentage of patients receiving each medication within each therapeutic class for the DB Safety Population. Multiple medication use by a patient will only be counted once.

The use of rescue medications during the OLTP and DBTP will be summarized by treatment group and generic terms for the following rescue medication categories in the safety population.

- Insomnia
- Extrapyramidal symptoms (EPS) or akathisia
- Agitation, Restlessness, and Hostility

The *WHO Drug Dictionary Enhanced*, version March 2017 or newer, will be used to classify prior and concomitant medications by therapeutic class and drug name.

9.0 EXTENT OF EXPOSURE AND TREATMENT COMPLIANCE

9.1 EXTENT OF EXPOSURE

Exposure to the OL IP for the OLTP will be summarized for treatment duration, calculated as the number of days from the date of the first dose of OL cariprazine taken to the date of the last dose taken during the OLTP, inclusive. Descriptive statistics (n, mean, SD, median, Q1, Q3, minimum, and maximum) will be presented.

Exposure to the DB IP for the DB Safety Population during the DBTP will be summarized for treatment duration, calculated as the number of days from the date of the first dose of DB IP to the date of the last dose of DB IP, inclusive. Descriptive statistics (n, mean, SD, median, Q1, Q3, minimum, and maximum) will be presented by treatment group.

Exposure to cariprazine during the entire study (OLTP and DBTP) will be summarized by intervals for the OL Safety Population. Descriptive statistics (n, mean, SD, median, Q1, Q3, minimum and maximum) will be presented.

By design, patients will take a fixed dose of cariprazine and there is no titration period during the DBTP. Mean daily dose, final dose will not be provided during the DBTP.

Patient-years, defined as exposure to the IP in years, will be summarized for the OLTP for the OL Safety Population. Patient-years will also be summarized by treatment group for the DBTP for the DB Safety Population. Patient years of exposure to cariprazine during the entire study (OLTP and DBTP) will also be summarized for the OL Safety Population.

